#### 4.3 Study Enrollment Procedures

- 4.3.1 Prior to implementation of this protocol, and any subsequent full version amendments, each site must have the protocol and the protocol consent form(s) approved, as appropriate, by their local institutional review board (IRB)/ethics committee (EC) and any other applicable regulatory entity (RE). Upon receiving final approval, sites will submit all required protocol registration documents to the DAIDS Protocol Registration Office (DAIDS PRO) at the Regulatory Support Center (RSC). The DAIDS PRO will review the submitted protocol registration packet to ensure that all of the required documents have been received.

Site-specific informed consent forms (ICFs) *WILL* be reviewed and approved by the DAIDS PRO, and sites will receive an Initial Registration Notification from the DAIDS PRO that indicates successful completion of the protocol registration process. A copy of the Initial Registration Notification should be retained in the site's regulatory files.

Upon receiving final IRB and any other applicable RE approvals for an amendment, sites should implement the amendment immediately. Sites are required to submit an amendment registration packet to the DAIDS PRO at the RSC. The DAIDS PRO will review the submitted protocol registration packet to ensure that all required documents have been received. Site-specific ICF(s) *WILL NOT* be reviewed and approved by the DAIDS PRO, and sites will receive an Amendment Registration Notification when the DAIDS PRO receives a complete registration packet. A copy of the Amendment Registration Notification should be retained in the site's regulatory files.

For additional information on the protocol registration process and specific documents required for initial and amendment registrations, refer to the current version of the DAIDS Protocol Registration Manual.

Once a candidate for study entry has been identified, details will be carefully discussed with the participant. The participant (or, when necessary, the legal

representative if the participant is under guardianship) will be asked to read and sign the approved protocol consent form.

For participants from whom a signed informed consent has been obtained, an ACTG Screening Checklist must be entered through the DMC Subject Enrollment System.

#### 4.3.2 Protocol Activation

Prior to enrollment, sites must complete the Protocol Activation Checklist found on the ACTG Member website. This checklist must be approved prior to any screening of participants for enrollment.

#### 4.3.3 Randomization

For participants from whom informed consent has been obtained, but who are deemed ineligible or who do not enroll into the initial protocol step, an ACTG Screening Failure Results form must be completed and keyed into the database.

Participants who meet the enrollment criteria will be randomized to the study according to standard ACTG DMC procedures.

### 4.4 Co-enrollment Guidelines

Sites are encouraged to co-enroll participants in A5128, “Plan for Obtaining Informed Consent to Use Stored Human Biological Materials (HBM) for Currently Unspecified Analyses.” Co-enrollment in A5128 does not require permission from the A5370 protocol chairs.

Co-enrollment with A5332 (REPRIEVE) and substudies of REPRIEVE- A5333s and A5361s- will be permitted as long as A5332 participants have reached the 1 year visit for that study.

For specific questions and approval for co-enrollment in other studies, sites should first check the A5370 PSWP or contact the protocol team via e-mail as described in the [Study Management](#) section.

## 5.0 STUDY INTERVENTION

Study treatment is defined as two infusions of REGN2810 (cemiplimab) or placebo. cART will not be provided by the study.

### 5.1 Intervention, Administration, and Duration

#### 5.1.1 Regimens

Forty-five HIV-1-infected participants will be sequentially assigned to one of three cohorts, beginning with the lowest dose cohort:

Cohort 1: Participants will receive 0.3 mg/kg of REGN2810 (cemiplimab) or placebo, administered at entry/day 0 and week 6 for a total of two infusions.

Cohort 2: Participants will receive 1 mg/kg of REGN2810 (cemiplimab) or placebo, administered at entry/day 0 and week 6 for a total of two infusions.

Cohort 3: Participants will receive 3 mg/kg of REGN2810 (cemiplimab) or placebo, administered at entry/day 0 and week 6 for a total of two infusions.

#### 5.1.2 Administration

REGN2810 (cemiplimab)/placebo infusion will occur over 30 minutes via intravenous (IV) infusion.

REGN2810 (cemiplimab) or diluent for REGN2810 (placebo) will be administered as an intravenous infusion mini-bag piggybacked onto a primary line of 0.9% sodium chloride for injection, USP. After infusing the REGN2810 (cemiplimab) or placebo for REGN2810 (cemiplimab) (diluent for REGN2810), flush the IV tubing with 0.9% sodium chloride for injection, USP.

Administration of intravenous REGN2810 (cemiplimab) or diluent for REGN2810 (cemiplimab) must include the use of a sterile, non-pyrogenic, low-protein binding 0.2 micron to 5 micron in-line or add-on filter is required for dosing. The total volume of the infusion will vary with the dose and participant weight. The infusion rate will vary based on the total volume needed to administer the full dose. Infusion access should be maintained and the participant observed for a minimum of 2 hours following completion of the first infusion and for a minimum of 30 minutes following the second infusion (see [section 8.0](#) for further detail).

#### 5.1.3 Duration

Participants will be followed for a total of 48 weeks after the first infusion of study drug.

## 5.2 Study Product Formulation and Preparation

REGN2810 (cemiplimab) (50 mg/mL) is formulated in an aqueous buffered solution at pH 6.0 containing 10 mM histidine, 5% (w/v) sucrose, 1.5% (w/v) L proline, and 0.2% (w/v) polysorbate 80. REGN2810 drug product is supplied as a sterile liquid solution of 5.5 mL in a 20 mL glass vial for IV administration. A volume of 5.0 mL can be withdrawn from each vial. Vials are for single use only.

Diluent for REGN2810 (cemiplimab) is an aqueous buffered solution at pH 6.0 containing 10 mM histidine, 5% (w/v) sucrose, 1.5% (w/v) L proline, and 0.2% (w/v) polysorbate 80. Diluent for REGN2810 (cemiplimab) will be used for 0.3 mg/kg cohort to prevent REGN2810 (cemiplimab) from binding to the bags and tubing when the REGN2810 (cemiplimab) is at low concentrations. Diluent for REGN2810 (cemiplimab) will also be used for the placebo for REGN2810 (cemiplimab) in all dose cohorts.

Store REGN2810 (cemiplimab) vials and diluent for REGN2810 (cemiplimab) vials at 2°C to 8°C.

Any unused portion of a REGN2810 (cemiplimab) vial will not be used for another participant.

The nurse responsible for administration and another clinician will each check the bag label and confirm that the identifier is correct and that the correct total milligrams to be administered is shown based on participant weight and the assigned mg/kg dose before beginning the IV administration.

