### 5.2.1 REGN2810 (cemiplimab) 0.3 mg/kg Dose Cohort: Preparation for Intravenous Administration

The REGN2810 (cemiplimab) 0.3 mg/kg dose cohort requires the use of the diluent for REGN2810 (cemiplimab). REGN2810 (cemiplimab) must NOT be diluted lower than 1.0 mg/mL without adding diluent.

Preparation of REGN2810 (cemiplimab) for IV administration will require either sterile empty IV bags made of polyvinyl chloride (PVC) or polyolefin (polyethylene and polypropylene) or 25 mL bags of 0.9% sodium chloride for injection, USP (normal saline), REGN2810 (cemiplimab) and diluent for REGN2810 (cemiplimab).

For each IV infusion order, the participant's weight and assigned treatment dose will be included in the pharmacy order.

1. Remove the vial(s) of REGN2810 (cemiplimab) and diluent from the refrigerator.
2. Observe vial(s) for damages, discoloration or particles.
3. Using aseptic technique in compliance with USP <797>

- a. Add 25 mL of 0.9% sodium chloride for injection, USP to the empty sterile IV bag (or start with a pre-made, commercially available 25 mL bag of 0.9% sodium chloride for injection, USP).
- b. Add 1 mL of diluent for REGN2810 (cemiplimab) to the bag. Invert the bag 10 times to mix thoroughly.
- c. Using a 1 mL polypropylene syringe for volumes less than 0.8 mL or a 3 mL polypropylene syringe for larger volumes, withdraw the correct volume of REGN2810 (cemiplimab) from the REGN2810 (cemiplimab) vial for the participant's weight based on [Table 5.2.2-1](#) below.
- d. Add the appropriate volume of REGN2810 (cemiplimab) to the IV bag then invert the IV bag 10 times to ensure that the investigational product and 0.9% sodium chloride are well mixed.

4. Label the IV bag with patient identifier, protocol number, REGN2810 (cemiplimab) x (mg) or placebo for REGN2810 (cemiplimab) in 0.9% sodium chloride Injection, USP, the final volume of the bag, final concentration, directions to infuse intravenously over 30 minutes the entire contents of the infusion bag plus sufficient volume of 0.9% sodium chloride Injection, USP to flush the tubing, preparation date and time, expiration time of 8 hours after dilution if stored at controlled room temperature (15°C to 25°C) or 24 hours if refrigerated at 2°C to 8°C, Investigational Use Statement ("Limited by Federal Law to Investigational Use"), and manufacturer information.

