#### 5.2.2 Placebo for REGN2810 (cemiplimab) 0.3 mg/kg Dose Cohort: Preparation for Intravenous Administration

Placebo for REGN2810 (cemiplimab) 0.3 mg/kg requires the use of two volumes of the diluent for REGN2810 (cemiplimab), the first as the diluent (1 mL per bag) and the second as placebo for REGN2810 (cemiplimab) calculated volume based on the participant's weight (0.006 mL/kg).

Preparation of placebo REGN2810 (cemiplimab) for IV administration will require either sterile empty IV bags made of PVC or polyolefin (polyethylene and polypropylene) or 25 mL bags of 0.9% sodium chloride for injection, USP (normal saline), and diluent for REGN2810 (cemiplimab).

For each IV infusion order, the participant's weight and assigned treatment dose will be included in the pharmacy order.

1. Remove the vial of diluent for REGN2810 (cemiplimab) from the refrigerator.
2. Observe vial for damages, discoloration or particles.
3. Using aseptic technique in compliance with USP <797>

- a. Add 25 mL of 0.9% sodium chloride for injection, USP to the empty sterile IV bag (or start with a pre-made, commercially available 25 mL bag of 0.9% sodium chloride for injection, USP)
- b. Add to the bag the:
  - i. 1 mL of diluent for REGN2810 (cemiplimab) plus
  - ii. Correct volume of diluent for REGN2810 (cemiplimab) for the participant's weight based on [Table 5.2.2-1](#) below.
4. Invert the bag 10 times to mix thoroughly to ensure the investigational product and 0.9% sodium chloride are well mixed.
5. Label the IV bag with patient identifier, protocol number, REGN2810 (cemiplimab) x (mg) or placebo for REGN2810 (cemiplimab) in 0.9% sodium chloride Injection, USP, the final volume of the bag, final concentration, directions to infuse intravenously over 30 minutes the entire contents of the infusion bag plus sufficient volume of 0.9% sodium chloride Injection, USP to flush the tubing, preparation date and time, expiration time of 6 hours after dilution if stored at controlled room temperature (15°C to 25°C) or 24 hours if refrigerated at 2°C to 8°C, Investigational Use Statement ("Limited by Federal Law to Investigational Use"), and manufacturer information.

If using a commercially available 25 mL mini-bag of 0.9% sodium chloride, USP then the final concentration must be calculated based on the best estimate of the total volume.

Expiration time includes the duration of infusion.

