#### Weight

Weight in kilograms (kg) should be assessed at screening, entry, weeks 6, 12, and 48. Weight should be documented prior to dosing, and the first infusion dose will be based on weight from entry. Week 6 dosing should also be based on weight from the entry visit unless there is a >10% change in body weight, in which case the dose should be adjusted accordingly.

Post entry, see [section 8.8](#) for collection requirements for pregnancy.

Post entry, record the following targeted event(s) regardless of grade:

- Uterine pregnancy
- Autoimmune diseases
- Immune deficiency syndromes
- All potential irAEs including but not limited to pneumonitis, colitis, hypothyroidism, hyperthyroidism, adrenal insufficiency, diabetes, hypophysitis, allergic skin reaction.
- Cancers
- Tuberculosis
- AIDS-defining conditions

Refer to [section 7.2](#) for AE collection requirements.

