### 10.4 Sample Size and Accrual

The total sample size of this study is 45 evaluable participants. Within each dose cohort, there will be 12 active-treated participants and 3 placebo participants. Ultimately, there will be a total of nine placebo recipients for comparison of immunologic and virologic outcomes. Participants who do not receive study treatment will be replaced. In addition, any participant who does not receive  $\geq 90\%$  of both study treatment infusions, or discontinues the study prior to week 12 without having met the primary safety endpoint ([section 10.2.1.1](#)), will be replaced.

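### Three total bag volumes in the 0.3 mg/kg preparation table are wrong, two of them by about 3 mL, and the two-person label check does not name the table it should be made against

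*Protocol*

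**What the plan says.** Section 5.1.1 sets the dose: "Cohort 1: Participants will receive 0.3 mg/kg of REGN2810 (cemiplimab) or placebo". Section 5.2 gives the vial strength: "REGN2810 (cemiplimab) (50 mg/mL) is formulated in an aqueous buffered solution". Under section 5.2.1 the preparer starts with 25 mL of saline, then follows the instruction "Add 1 mL of diluent for REGN2810 (cemiplimab) to the bag", and finally must "withdraw the correct volume of REGN2810 (cemiplimab) from the REGN2810 (cemiplimab) vial for the participant's weight based on" Table 5.2.2-1. That table is entered by 10 kg weight band. It prints the dose in mg, the drug volume, the total volume in the bag and the concentration.

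The total volume is used in several places. Sections 5.2.1 and 5.2.2 put the final volume and concentration on the bag label. Section 5.1.2 makes the infusion rate depend on total volume, with a 30-minute infusion. Section 6.3.5 requires the bag volume, concentration and rate to be recorded.

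Before the infusion starts, section 5.2 has the nurse and a second clinician each confirm that "the correct total milligrams to be administered is shown based on participant weight and the assigned mg/kg dose". That sentence mentions neither the band tables nor a tolerance.

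**The concern.** A preparation table should be consistent within each row: the components should add to the total, and total times concentration should return the dose. Three rows of Table 5.2.2-1 fail the first test, and two of them clearly fail the second. A pharmacist who copies the printed total onto the label, or a nurse who sets the pump from it, works from a volume that the bag does not hold. For a commercial mini-bag the concentration is to be worked out from the best estimate of total volume, so a preparer who starts from the printed total would also get the wrong concentration.

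The second matter is the wording of the bedside check. Bags are made to banded doses, while the check is described in terms of the participant's weight and the mg/kg dose. Someone who multiplies the two will often get a figure that differs from a correct label, and the text does not say which figure governs.

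**Working it through.** **Inputs.** Vial strength 50 mg/mL (section 5.2); 25 mL saline and 1 mL diluent (section 5.2.1); doses, drug volumes, totals and concentrations from Table 5.2.2-1.

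**Formulas.** Drug volume = dose / 50. Total = 25 + 1 + drug volume. Concentration = dose / total.

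**Reproducing a sound row.** For 50 to <60 kg: 16/50 = 0.32 mL; 25 + 1 + 0.32 = 26.32 mL; 16/26.32 = 0.608, printed as 0.61 mg/mL. All three figures agree with the table. Across the table, every drug volume equals dose/50, and 12 of the 15 totals reproduce exactly.

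**The three rows that do not.**

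| Band | Dose | Drug volume | Printed total | Correct total | Difference | Printed conc. | Dose / correct total | Dose / printed total |
|---|---|---|---|---|---|---|---|---|
| 120 to <130 kg | 37 mg | 0.74 mL | 26.72 mL | 26.74 mL | -0.02 mL | 1.38 | 1.384 | 1.385 |
| 150 to <160 kg | 46 mg | 0.92 mL | 29.91 mL | 26.92 mL | +2.99 mL | 1.71 | 1.709 | 1.538 |
| 160 to <170 kg | 49 mg | 0.98 mL | 29.98 mL | 26.98 mL | +3.00 mL | 1.82 | 1.816 | 1.634 |

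Relative size: 2.99/26.92 = 11.1% and 3.00/26.98 = 11.1%; in the first row, 0.02/26.74 = 0.07%. In the two 3 mL rows the printed concentration fits only the corrected total, so the total is the faulty cell. In the 120 kg row the rounded concentration cannot tell the two totals apart; the error shows only in the sum.

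**Effect on infusion time.** A rate set to deliver 29.91 mL in 30 minutes is 29.91/30 = 0.997 mL/min. The actual 26.92 mL then runs out in 26.92/0.997 = 27.0 minutes. For the next row, 30 x 26.98/29.98 = 27.0 minutes.

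**Cohorts 2 and 3.** All 60 printed concentrations in Tables 5.2.4-1 and 5.2.6-1 reproduce as dose / (25 + dose/50).

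**The bedside check read literally.** Weight times mg/kg against the tabulated dose:

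- Cohort 1, 50 kg: 0.3 x 50 = 15.0 mg against 16 mg; the label is 6.7% above.
- Cohort 1, 59 kg: 0.3 x 59 = 17.7 mg against 16 mg.
- Cohort 1, just under 60 kg: about 18 mg against 16 mg; the label is 11.1% below, the largest gap in any table.
- Cohort 2, just under 55 kg: about 55 mg against 50 mg; the label is 9.1% below. Cohort 3 gives the same percentage (about 165 mg against 150 mg).

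The gaps narrow as weight rises. In the top band they are +1.8% to -3.3% in Cohort 1 and 0 to -2.5% in Cohorts 2 and 3.

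**The case against.** The strongest reply is that no participant's dose is wrong. In all three rows the milligrams, the drug volume and the concentration are right; one error is 0.02 mL; and the other two apply only at 150 to <170 kg in a planned cohort of 15. All of that stands, and it limits the weight of the point. It does not make the cells correct.

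On the bedside check, the protocol never tells staff to multiply. Each table is titled as a dose calculation table, is entered by weight band and carries a dose column, so reading the check as a look-up by weight and cohort is fair, and on that reading a correct label agrees exactly. A reader might infer that the check cannot agree with a correctly made bag, or that sites will override it routinely. The text does not support the first, and the second is conjecture. What remains is that the sentence could name the table and does not.

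Other inferences are tempting and should not be drawn:

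- **The 90% rule.** A fully infused bag is 26.92/29.91 = 90.0% or 26.98/29.98 = 89.99% of the printed total, which seems to touch the rule under which a participant "will be replaced" (section 10.4) or leaves the efficacy set (section 10.6.2). Neither section measures completion against the printed total. The label directs that the whole bag be infused, and section 6.3.5 records whether the full dose was given.
- **Banding.** Different bands in different cohorts are an openly printed design choice, and nothing in the protocol requires one convention.
- **Placebo volume.** Section 5.2.2 speaks of a "calculated volume based on the participant's weight (0.006 mL/kg"), but this is only 0.3 mg/kg divided by 50 mg/mL, stated by way of introduction. The preparation step itself sends the preparer to the table.
- **Entry weight.** Section 6.3.4 is explicit: "Week 6 dosing should also be based on weight from the entry visit unless there is a >10% change in body weight". That is a default with an exception, and it does not contradict the table header.
- **Expiry.** A bag held while a mismatch is queried is not confined to the room-temperature limit, because the labels also allow 24 hours refrigerated.

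**Conclusion.** The point holds as a minor correction. Three printed totals in Table 5.2.2-1 are wrong by -0.02, +2.99 and +3.00 mL, and the two larger ones, each 11.1% too high, contradict the concentrations beside them. The possible consequences are a wrong final volume on the label, a wrong recorded volume and an infusion about 3 minutes short, for participants of 150 to <170 kg in the 0.3 mg/kg cohort. These arise only if staff rely on the printed total. The number of participants in that range is not known from the protocol and is likely to be small.

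The check in section 5.2 is loosely worded and does not amount to a failed safeguard. Its wording matters only to someone who calculates instead of looking up, for whom the gap reaches about 11%. Neither matter affects the milligram dose, the sample size or any analysis.

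**What to change.** In Table 5.2.2-1, correct the totals to 26.74 mL (120 to <130 kg), 26.92 mL (150 to <160 kg) and 26.98 mL (160 to <170 kg). Leave the doses, drug volumes and concentrations in those rows as they are.

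In section 5.2, reword the two-person check so that the label is confirmed against the tabulated dose in mg for the participant's weight band and cohort, with Tables 5.2.2-1, 5.2.4-1 and 5.2.6-1 named.

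The cost is a clarification memo to site pharmacies and clinics and three changed cells. Visits, sample size and analyses are unaffected.

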### 5.2.1 REGN2810 (cemiplimab) 0.3 mg/kg Dose Cohort: Preparation for Intravenous Administration

The REGN2810 (cemiplimab) 0.3 mg/kg dose cohort requires the use of the diluent for REGN2810 (cemiplimab). REGN2810 (cemiplimab) must NOT be diluted lower than 1.0 mg/mL without adding diluent.

Preparation of REGN2810 (cemiplimab) for IV administration will require either sterile empty IV bags made of polyvinyl chloride (PVC) or polyolefin (polyethylene and polypropylene) or 25 mL bags of 0.9% sodium chloride for injection, USP (normal saline), REGN2810 (cemiplimab) and diluent for REGN2810 (cemiplimab).

For each IV infusion order, the participant's weight and assigned treatment dose will be included in the pharmacy order.

1. Remove the vial(s) of REGN2810 (cemiplimab) and diluent from the refrigerator.
2. Observe vial(s) for damages, discoloration or particles.
3. Using aseptic technique in compliance with USP <797>

- a. Add 25 mL of 0.9% sodium chloride for injection, USP to the empty sterile IV bag (or start with a pre-made, commercially available 25 mL bag of 0.9% sodium chloride for injection, USP).
- b. Add 1 mL of diluent for REGN2810 (cemiplimab) to the bag. Invert the bag 10 times to mix thoroughly.
- c. Using a 1 mL polypropylene syringe for volumes less than 0.8 mL or a 3 mL polypropylene syringe for larger volumes, withdraw the correct volume of REGN2810 (cemiplimab) from the REGN2810 (cemiplimab) vial for the participant's weight based on [Table 5.2.2-1](#) below.
- d. Add the appropriate volume of REGN2810 (cemiplimab) to the IV bag then invert the IV bag 10 times to ensure that the investigational product and 0.9% sodium chloride are well mixed.

4. Label the IV bag with patient identifier, protocol number, REGN2810 (cemiplimab) x (mg) or placebo for REGN2810 (cemiplimab) in 0.9% sodium chloride Injection, USP, the final volume of the bag, final concentration, directions to infuse intravenously over 30 minutes the entire contents of the infusion bag plus sufficient volume of 0.9% sodium chloride Injection, USP to flush the tubing, preparation date and time, expiration time of 8 hours after dilution if stored at controlled room temperature (15°C to 25°C) or 24 hours if refrigerated at 2°C to 8°C, Investigational Use Statement ("Limited by Federal Law to Investigational Use"), and manufacturer information.

If using a commercially available 25 mL mini-bag of 0.9% sodium chloride, USP then the final concentration must be calculated based on the best estimate of the total volume.

Expiration time includes the duration of infusion.

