#### 6.2.5 Discontinuation Evaluations

Evaluations for Randomized Participants Who Do Not Start Study Treatment

Participants who withdraw from the study prior to starting study treatment/placebo should have entry/day 0 and off-study forms completed and keyed. No further evaluations or follow-up are required for these participants. Participants will be replaced. All eCRFs must be completed for the period up to and including entry/day 0.

Premature Treatment/Placebo Discontinuation Evaluations

Participants who begin but do not complete of both infusions of cemiplimab/placebo, but receive some of the investigational product, and are willing to stay on the study, will be followed for safety by completing all study visits and evaluations as outlined in the SOE. If one or both cemiplimab/placebo infusions have been administered, samples for serum cemiplimab, RO, and ADA will be collected per the SOE (duration of sampling in participants that do not receive or complete the second infusion will be decided on a case-by-case basis with the core team). Whether virologic, immunologic, and stored ARV plasma samples will be stored or performed following premature discontinuation of cemiplimab/placebo infusions will be determined on a case-by-case basis in discussion with the core team. The duration of the infusion (including actual start and stop times) and the volume of each cemiplimab/placebo infusion should be recorded. Participants who do not complete  $\geq 90\%$  of both infusions of cemiplimab/placebo will be replaced unless the participant has reached a protocol-defined safety endpoint. Participants who withdraw should be explicitly asked about the contribution of possible AEs to their decision to withdraw consent, and any AE information elicited should be documented.

Discontinuation of Antiretroviral Therapy

Participants who discontinue cART for any reason will be followed for safety by completing all study visits and evaluations as outlined in the SOE. If ART is discontinued prior to completion of cemiplimab/placebo infusions, then no further infusions should be given. Whether cemiplimab serum concentrations or RO assays will be collected following discontinuation of ART will be determined on a case-by-case basis in discussion with the core team. Stored plasma/PBMC for

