### 7.2 AE Collection Requirements for This Protocol

Post-entry, all AEs must be recorded on the eCRFs if any of the following criteria have been met.

- All Grade  $\geq 1$  AEs
- All suspected or confirmed irAEs
- All infusion reactions
- All AEs that led to a change in study intervention
- All AEs meeting SAE definition or Expedited Adverse Event (EAE) reporting requirement
- All targeted events listed in [section 6.3.4](#)

NOTE: SAEs or events meeting EAE reporting requirements should also be entered into the DAIDS Adverse Experience Reporting System (DAERS), an Internet-based reporting system. All SAEs, irAEs, and AESIs will be recorded in DAERS, regardless of causality.

All AEs that are reported must have their severity graded. To grade AEs, sites must refer to the Division of AIDS Table for Grading the Severity of Adult and Pediatric Adverse Events (DAIDS AE Grading Table), corrected Version 2.1, July 2017, which can be found on the DAIDS RSC website at <https://rsc.niaid.nih.gov/clinical-research-sites/daids-adverse-event-grading-tables>.

Infusion reactions, adrenal insufficiency, and pneumonitis should be graded per the National Cancer Institute's (NCI) Common Terminology Criteria for AEs (CTCAE) guidelines as outlined in [section 8.0](#), and can also be found in the National Cancer Institute's Table for CTCAE, version 5.0, found on the National Cancer Institute Web site:  
[https://ctep.cancer.gov/protocolDevelopment/electronic\\_applications/docs/CTCAE\\_v5\\_Quick\\_Reference\\_5x7.pdf](https://ctep.cancer.gov/protocolDevelopment/electronic_applications/docs/CTCAE_v5_Quick_Reference_5x7.pdf)

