## 7.4 Study Monitoring

The Protocol Core Team will monitor the conduct and safety of the study via regular summaries by cohort pooled over treatment arms of accrual, baseline characteristics, study conduct (including premature study discontinuations and premature study treatment discontinuations), any missed doses of study treatment/placebo, any reported interruptions of ART, HIV-1 RNA levels  $\geq 200$  copies/mL (see [section 6.2.4/Confirmation of Virologic Failure](#)), data completeness, specimen collection, and AEs. The core protocol team will review the individual participant-level safety data frequently to assess the relation of all reported AEs to study treatment/placebo.

The DAIDS clinical representative will review and assess EAE reports for potential impact on the study participant safety and protocol conduct as per DAIDS policies, guidance documents, and SOPs, as applicable.

The study will undergo interim review at least annually by an independent ACTG-appointed SMC. The first review is anticipated to be review of the first cohort, regarding dose escalation to the second cohort. The SMC will review information by cohort on accrual, baseline characteristics, conduct of the study (including premature study discontinuations and premature study treatment discontinuations), AEs by treatment arm (including core protocol team assessment of relationship to study treatment), CD4+ T cell counts, virologic failures, and HIV-1 RNA levels/suppression over time by treatment arm, and completeness of follow-up and sample availability. In particular, irAEs will be monitored.

After the last enrolled participant in each cohort receives study treatment and completes follow-up through the week 12 visit and the blinded data become available for review by the core team, safety data including the core team decision on relation of AEs to study treatment will be reviewed by the SMC, unblinded to treatment arm, to determine whether to dose escalate or modify the study. Complementing the SMC reviews, a designated study chair or co-chair may notify the SMC of Grade 4 AEs or deaths, as well as notable Grade 3 AEs among the events that the sites email to the core team per section 8.0. An interim review may also be convened if a concern is identified by the DAIDS clinical representative, the study chairs, or study statisticians in consultation with the team. See also [section 10.4](#) for statistical considerations related to interim monitoring.

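### Cohort 1 bag labels: 8-hour room-temperature expiration for active but 6 hours for placebo, a probable one-digit slip that puts an arm-specific cue on a masked label

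*Protocol*

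**What the plan says.** Sections 5.2.1 to 5.2.6 of the protocol describe six preparations, active and placebo at each of three dose levels. Each has a labelling step that sets an expiration time.

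- Section 5.2.1 (0.3 mg/kg active): "expiration time of 8 hours after dilution if stored at controlled room temperature".
- Section 5.2.2 (0.3 mg/kg placebo): "expiration time of 6 hours after dilution if stored at controlled room temperature".
- Sections 5.2.3 to 5.2.6 (1 and 3 mg/kg, active and placebo): 6 hours.

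All six allow 24 hours under refrigeration, and all count the infusion itself within the limit. The label is meant to hide the arm. In both Cohort 1 instructions the product line is the milligram amount "or placebo for REGN2810 (cemiplimab) in 0.9% sodium chloride Injection, USP, the final volume of the bag, final concentration", followed later by the preparation date and time. Section 5.2 requires the administering nurse and a second clinician to check the label before each infusion. Section 3.0 states that the trial is double-blinded within each cohort.

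**The concern.** The two values that disagree belong to the two arms of one blinded cohort. Expiration time minus preparation time, both printed on the bag, would be 8 hours for active and 6 hours for placebo. Sections 5.2.1 and 5.2.2 are headed by arm, so the protocol itself gives the key. Cohorts 2 and 3 have no such cue, because both arms there carry 6 hours.

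What is exposed is the site's part of safety assessment in Cohort 1: noticing events, grading them and attributing them for the first time. Section 7.2 leaves grading to the sites: "All AEs that are reported must have their severity graded. To grade AEs, sites must refer to the Division of AIDS Table".

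There is also a plain handling question. If 6 hours is the correct limit, the text as written lets Cohort 1 active bags be used up to 2 hours too late.

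**Working it through.** No statistical calculation applies. The check is a comparison of the text, followed by simple counts.

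**1. The six expiration times**

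| Section | Preparation | Room temperature | Refrigerated |
|---|---|---|---|
| 5.2.1 | 0.3 mg/kg active | 8 h | 24 h |
| 5.2.2 | 0.3 mg/kg placebo | 6 h | 24 h |
| 5.2.3 | 1 mg/kg active | 6 h | 24 h |
| 5.2.4 | 1 mg/kg placebo | 6 h | 24 h |
| 5.2.5 | 3 mg/kg active | 6 h | 24 h |
| 5.2.6 | 3 mg/kg placebo | 6 h | 24 h |

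One of six says 8 hours and five say 6.

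**2. Slip or intention?** The label sentences in 5.2.1 (step 4) and 5.2.2 (step 5) have 101 words each. Of these, 100 match and one differs, the 8 against the 6. The protocol gives no reason for a difference. The direction is also odd. The placebo bag holds no antibody, so antibody stability cannot explain its shorter limit. The 0.3 mg/kg active bag is the one for which section 5.2 adds diluent, because at low concentration the antibody binds to bags and tubing. Yet it has the longest limit.

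**3. When the cue would work.** Two conditions must both hold: the bag shows the room-temperature limit (the 24-hour limit is the same in both arms), and the reader knows which interval belongs to which arm. If both held for every Cohort 1 bag, the arm could be read for 15 of 15 planned participants. Guessing active every time would be right for 12 of 15 (80%).

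**4. Exposure.** Planned infusions in Cohort 1: 12 × 2 + 3 × 2 = 24 + 6 = 30.

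This is not a ceiling. Section 6.2.5 says participants who do not complete at least 90% "of both infusions of cemiplimab/placebo will be replaced unless the participant has reached a protocol-defined safety endpoint". Section 10.4 has the same rule and adds early leavers: at least 90% "of both study treatment infusions, or discontinues the study prior to week 12 without having met the primary safety endpoint". With r participants replaced after dosing, 15 + r are dosed and there are 30 + r to 30 + 2r infusions. The protocol gives no figure for r; the range 1 to 3 is an assumption.

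| r | Dosed | Infusions |
|---|---|---|
| 1 | 16 | 31–32 |
| 2 | 17 | 32–34 |
| 3 | 18 | 33–36 |

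Nor is 30 a floor, because someone who stops after the first infusion with a safety endpoint is not replaced. The share of bags that would show the room-temperature limit is not stated and may be 0.

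**The case against.** Four points can be made for leaving the text alone.

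- **One digit of text read from a PDF.** Table 5.2.2-1 also has totals that do not add up: for 150 to <160 kg, 25 + 1 + 0.92 = 26.92 mL, printed as 29.91 mL. Those could be protocol errors or reading errors, and an 8 read for a 6 cannot be excluded. This stands, and it is why confidence is only medium.
- **The preparations differ.** The 0.3 mg/kg active bag contains drug plus added diluent, and a true 8-hour limit is possible. Five-to-one agreement does not prove which value is right, and the pharmacy manual cited in section 5.3 is not at hand. This stands too, but it does not rescue the text: under a within-cohort blind the two Cohort 1 labels must match whichever value is correct.
- **The cue is conditional.** It needs the room-temperature limit on the bag and a reader who knows the rule. This stands and limits the size of the problem.
- **The trial's main judgements are protected.** Section 7.4 says "The core protocol team will review the individual participant-level safety data frequently to assess the relation of all reported AEs to study treatment/placebo", and section 10.2.1.1 makes that team's blinded judgement part of the primary outcome. The SMC is already unblinded when it advises on escalation. All Grade 1 or higher events are recorded, and section 7.2 adds: "All SAEs, irAEs, and AESIs will be recorded in DAERS, regardless of causality". This largely stands. It is not complete protection: section 7.3.2 limits the expedited-reporting rule for AESIs to those felt to be related, so first attribution at the site keeps some role.

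**Conclusion.** The inconsistency is real on the text available, and nothing in the protocol reconciles it. It is minor. The gap is 2 hours, in one cohort, on at most the Cohort 1 bags that show a room-temperature limit. The likely consequence is a small risk to site-level detection, grading and first attribution of adverse events. The core team's blinded judgement of relatedness and the SMC's unblinded review are not directly affected.

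The conclusion assumes that the printed 8 is what the protocol says. The view that it is a slip is an inference from the otherwise identical wording. The need for one common value does not depend on that inference.

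**What to change.** Confirm the digit against the source file, then set one room-temperature expiration for both Cohort 1 labels. Use 6 hours by default, which aligns section 5.2.1 with the other five preparations. Use 8 hours for both only if the sponsor's stability data support it. Issue a pharmacy memo so that sites apply the common value.

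The cost is one digit, the memo and 2 hours of shelf life for Cohort 1 active bags. Because the limit includes infusion time, the latest start after dilution changes as follows:

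- 30-minute infusion: from 8 − 0.5 = 7.5 h to 6 − 0.5 = 5.5 h.
- 3-hour infusion (the maximum in section 6.3.5): from 8 − 3 = 5 h to 6 − 3 = 3 h.

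No change to sample size or analysis is needed.
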